14.3.4 Adverse Events

All AEs will be collected and evaluated from the time the informed consent is signed throughout the duration of the study and up to the last observation in the study. AEs and SAEs will be reviewed at all scheduled and unscheduled study visits from the time the informed consent is signed. See [Section 16.0](#) for details regarding safety assessment and monitoring.

14.4 Pharmacokinetic Procedures

For subjects who are willing to participate in the PK sampling, up to three (3) blood samples should be collected at the following visits and sampling windows: Day 2 (one sample collected anytime post dosing), Days 3 to 5 (one sample collected predose on any of these days), and Days 7 to 10 (one sample collected predose on any of these days). Additional blood PK samples will be collected when clinically indicated.

Procedures for collecting, storing, and shipping plasma samples for PK are described in the study PK Manual. The sparse samples collected in this study will be analyzed using Population PK (Pop PK) analysis methods to estimate PK parameters (C_{max} , AUC, clearance/fraction absorbed [CL/F]) as applicable. Further analysis of possible metabolites may be performed.

In addition to blood samples, other fluid and tissue samples may be collected for ibrexafungerp PK determination when clinically indicated. Tissue samples collected as part of SOC procedures (e.g., biopsies) may be sent for drug concentration analysis, when available.

15.0 Study Schedules

Detailed schedules of all study visits and procedures for all subjects (except VVC subjects) are presented in [Table 14](#) and detailed schedules of all study visits and procedures for VVC subjects are presented in [Table 15](#).

Table 14 Schedule of Treatment Visits and Procedures (All Fungal Diseases Except VVC)

PROCEDURE Visit	Screen ^a	BL/ D1 ^a	D2 (PK Only)	D3- D5	D7- D10	Study Day 14 and then Every 14 days during Tx	D42	D84 ^t	D90 ^u	D120	D180	EOT	Unsch. Visits	FU 1 ^b (6- WK)	FU 2- FU 3 ^b
Days (allowable window)	-1 (-3)	Prior to Tx		±2 d	±2 d	±2 d	±7 d	±7 d	±7 d	±14 d	±14 d	±3 d	AP	± 7d	AP
GENERAL															
Informed Consent	X														
Subject Enrollment and ID Assignment	X														
Medical History and Demographics	X														
Inclusion/Exclusion Criteria	X	X													
Pregnancy Test ^s	X												X		
Prior and Concomitant Medications	X													X	
Study Drug Dispensing ^c		X				X									
Study Drug Collection and Accountability Review						X							X	X	
Study Drug Dosing		X	X	X									X ^d		
Subject Diary Dispensing and Collection		X				X							X	X	
EFFICACY															
Targeted PE including S&S ^v	X	X				X	X ^d	X ^d	X ^{e,f}		X ^{e,f}	X ^d		X ^d	X ^f
Mycological Testing ^{g,j}	X ^d	X ^d				← X ^d →		X ^d	X ^e		X ^e	X ^d		X ^d	
Imaging ^h	X ^{d,r}						X ^d	X ^d	X ^{e,f}		X ^{e,f}	X ^{d,i}		X ^{d,i}	
Serological Testing ^{j,k}	X ^d	X ^d				← X ^d →	X ^d	X ^d	X ^{e,f}		X ^{e,f}	X ^d		X ^d	X ^f
Esophagoscopy ^l	X ^m						X ^l					X ^l	X ^l	X ^l	
Spirometry	X ^f	X ^f					X ^f								
SGRQ	X ^e	X ^e							X ^e		X ^e	X ^e		X ^e	
6-Minute Walk Test	X ^e	X ^e							X ^e		X ^e				
MRC Dyspnea Scale	X ^e	X ^e							X ^e		X ^e				

PROCEDURE Visit	Screen ^a	BL/ D1 ^a	D2 (PK Only)	D3- D5	D7- D10	Study Day 14 and then Every 14 days during Tx	D42	D84 ^t	D90 ^u	D120	D180	EOT	Unsch. Visits	FU 1 ^b (6- WK)	FU 2- FU 3 ^b
Days (allowable window)	-1 (-3)	Prior to Tx		±2 d	±2 d	±2 d	±7 d	±7 d	±7 d	±14 d	±14 d	±3 d	AP	±7d	AP
Assessment of Recurrence													X ^e		X
Subject Status (alive/ deceased)							X	X ^o	X ^{e,f}	X ^{e,f}	X ^{e,f}				
Assessment of Efficacy							X ^d	X ^d	X ^d			X ^d	X ^d	X ^d	X ^f
SAFETY															
Vital Signs	X	X										X ^p	X	X	
General Physical exam	X												X		X
Clinical Laboratory Safety Assessments	X					X ⁿ	X ⁿ	X ⁿ	X ^{n,e}	X ⁿ	X ^{n,e}	X	X ⁿ	X ⁿ	
AEs	X-----														X
PHARMACOKINETIC															
PK Assessments ^q			X	X	X										

Abbreviations: AE = adverse event; ABPA = allergic bronchopulmonary aspergillosis; AP = as applicable; CPA=chronic pulmonary aspergillosis; d = day; D = Day;

EC=esophageal candidiasis; eCRF=electronic case report form; EOT = End of Treatment; FU = Follow-up; ID = identification; IPA = invasive pulmonary aspergillosis; MRC = Medical Research Council; PK=pharmacokinetic; Screen. = Screening; S&S = signs and symptoms; SGRQ = St. George's Respiratory Questionnaire; Tx = treatment; Unsch. = unscheduled; W = Week.

Note: Study days, weeks and months are counted relative to the first dose of study drug (Baseline [Day 1]). For FU visits, weeks, months and years are counted relative to the EOT visit.

- a. Screening and Baseline (Day 1) may occur on the same day.
- b. FU visits will occur 6 weeks (6-Week FU = FU 1), 3 months (3-Month FU = FU 2) and 6 months (6-Month FU = FU 3) after the EOT visit. FU visits FU 2 and FU 3 will be conducted for ABPA subjects only.
- c. For subjects who are not hospitalized.
- d. As applicable based on fungal disease.
- e. For CPA subjects. Efficacy procedures for CPA subjects will be performed every 3 months following Day 180 if the subject is still on treatment.
- f. For ABPA subjects. Efficacy procedures for ABPA subjects will be performed every 3 months following Day 180 if the subject is still on treatment.
- g. For urinary tract infections, urine samples for fungal cultures are recommended to be collected every 48-72 hours until negative.
- h. In addition to the scheduled time points, imaging scans will be collected anytime during therapy, as clinically indicated.
- i. The window for EOT imaging may range from ± 3 to ± 7 days, depending on fungal disease.
- j. For subjects diagnosed exclusively by β-D-glucan tests, the diagnosis should be based on two consecutively positive T2 or β-D-glucan tests. For those subjects diagnosed based on positive T2 tests, samples for T2 testing will be collected every 48 hours until negative. For those subjects diagnosed based on positive β-D-glucan tests, samples for β-D-glucan testing will be collected every 72 hours until negative.
- k. For disseminated/invasive dimorphic fungi subjects, serological tests may be conducted at other time points, as clinically indicated.
- l. For EC subjects only. A repeat esophagoscopy is required at EOT for all subjects, if allowable per SOC practice. Additional esophagoscopies are recommended at the Day 42 and 6-Week FU visits only if symptoms have recurred and following local standard practices. Esophagoscopies should be performed at any unscheduled visits, if clinically indicated per local standard practices.

PROCEDURE Visit	Screen ^a	BL/ D1 ^a	D2 (PK Only)	D3- D5	D7- D10	Study Day 14 and then Every 14 days during Tx	D42	D84 ^t	D90 ^u	D120	D180	EOT	Unsch. Visits	FU 1 ^b (6- WK)	FU 2- FU 3 ^b
Days (allowable window)	-1 (-3)	Prior to Tx		±2 d	±2 d	±2 d	±7 d	±7 d	±7 d	±14 d	±14 d	±3 d	AP	± 7d	AP

- m. For subjects who have EC, results of the most recent esophagoscopy that confirmed the diagnosis must be available for Screening. A repeat esophagoscopy is not required at Screening if the subject's signs and symptoms of EC have persisted since initial diagnosis.
- n. If clinically indicated.
- o. For IPA subjects, subjects with disseminated/invasive dimorphic fungi and subjects with other emerging fungi.
- p. At Day 180, weight will be determined for CPA subjects only. No other vital sign measurements will be collected for CPA or any other subjects.
- q. Sparse PK samples for Population PK analysis will be collected during the following time windows on Day 2 (anytime post dosing); between Days 3 to 5 (predose) and between Days 7 to 10 (predose). Additional blood PK samples will be collected when clinically indicated. The time of dosing and sample collection must be recorded on the subject diary and eCRF. In addition to blood samples, other fluid and tissue samples may be collected for ibrexafungerp PK determination when clinically indicated. Tissue samples collected as part of SOC procedures (e.g., biopsies) may be sent for drug concentration analysis, when available.
- r. Baseline radiological assessments for invasive fungal disease should be performed ideally within 72 hours of Screening. However, assessments performed up to 7 days before/after the first administration of study medication may be used to confirm the diagnosis of the fungal disease if none exists within the ideal window.
- s. Pregnancy tests may be conducted more often (e.g., on a monthly basis), per local regulations.
- t. For CMC D84 is TOC unless EOT occurs first
- u. For CPA and ABPA D90 is TOC unless EOT occurs first
- v. Targeted Physical Examinations (clinical evaluation of signs and symptoms) should be performed if subject comes in for PK assessments

Table 15 Schedule of Treatment Visits and Study Procedures for VVC

Study Visit/ Day	Screen ^a	BL/ Day 1 ^a	D4	EOT D7	TOC D17	25- DAY FU D32 ^b	35- DAY FU ^c D42	Unsch Visits
Study Procedures	-1 (-3)	Prior to Tx		Phone/ On-site ^c	± 3 days		Phone/ On- site ^c	
GENERAL								
Informed Consent	X							
Subject Enrollment and ID Assignment	X							
Medical History and Demographics	X							
Inclusion/Exclusion Criteria	X	X						
Pregnancy Test	X							
Prior and Concomitant Medications	X-----X							X
Study Drug Dispensing		X						
Study Drug Collection and Review								
Subject Diary Dispensing and Collection		X			X			
EFFICACY								
Targeted PE including Clinical Evaluation of Signs and Symptoms of Infection	X	X		X	X	X	If applic. ^d	
Mycological Testing (fungal culture)	X	If applic.		X	X	X	If applic. ^d	If applic.
Assessment of Recurrence						X		
Subject Status (alive/ deceased)							X	
Assessment of Efficacy				X	X	X	X	
SAFETY								
Vital Signs	X	X		X				X
General Physical exam	X			X				
Clinical Laboratory Safety Assessments	X			X		X		If applic.
Adverse events	X-----X							
PHARMACOKINETIC								
PK Assessments ^e			X ^e	X ^e				

Abbreviations: applic. = applicable; BL = Baseline; D = day; eCRF = electronic case report Form; EOT = end of treatment; FU = Follow-up; ID = identification; PE = physical exam; PK = pharmacokinetic; Screen = Screening; TOC = test of cure; Tx = treatment; Unsch. = unscheduled.

a. Screening and Baseline/ Day 1 can occur on the same day.

b. The 25-Day FU visit will occur on study Day 32 (i.e., 32 days after the first dose of study drug and 25 days after EOT).

c. The 35-Day FU visit will occur on study Day 42 (i.e., 42 days after the first dose of study

Study Visit/ Day	Screen ^a	BL/ Day 1 ^a	D4	EOT D7	TOC D17	25- DAY FU D32 ^b	35- DAY FU ^c D42	Unsch Visits
Study Procedures	-1 (-3)	Prior to Tx		Phone/ On-site ^c	± 3 days		Phone/ On- site ^c	

drug and 35 days after EOT). This will be a telephone call and only a full on-site visit if the subject is symptomatic.

- d. Vaginal examination and samples for mycological testing to be done if the subject is still symptomatic.
- e. For subjects who give consent, sparse PK samples for Population PK analysis should be collected during the following time windows between Days 3 to 5 (predose) and between Days 7 to 10 (predose). The time of dosing and sample collection must be recorded on the subject diary and eCRF. Additional PK samples will be collected when clinically indicated.

16.0 Safety Assessments and Monitoring

16.1 Definition of an Adverse Event

An AE is any untoward medical occurrence associated with the use of a drug in humans, whether or not considered drug related. An AE can therefore be any unfavorable and unintended sign (including an abnormal laboratory finding), symptom or disease temporally associated with the use of a study drug/study intervention, whether or not related to the study drug/study intervention.

Any laboratory abnormality that is deemed to be clinically significant in the opinion of the Investigator will be considered an AE and should be recorded in the eCRF, whether or not it is related to the study drug. For non-fungal infection-related AEs (e.g., bacterial sepsis, bacterial intra-abdominal abscess) the positive cultures related to the AE should also be recorded on the eCRF.

Stable chronic conditions that are present prior to clinical trial enrollment and do not worsen are not considered AEs and will be accounted for in the subject's medical history.

The following can be considered AEs:

- An exacerbation of a pre-existing illness
- An increase in frequency or intensity of a pre-existing episodic event or condition
- A condition detected or diagnosed after the initiation of treatment with study medication, even though it may have been present prior to the start of the study
- Continuous persistent disease or symptoms present at Baseline (Day 1) that worsen after signing the informed consent or following the initiation of treatment with study medication

The following are **not** considered AEs:

- Medical or surgical procedures (e.g., surgery, endoscopy, tooth extraction or transfusion); the condition that leads to the procedure is an AE
- Pre-existing disease or conditions present or detected at the start of the study that do not worsen
- Situations where an untoward medical occurrence has not occurred (e.g., hospitalizations for cosmetic surgery or elective surgery or social/convenience admissions)
- The disease being studied or signs or symptoms associated with the disease, unless more severe than expected for the subject's condition or a worsening of the disease being studied

16.2 Definition of a Serious Adverse Event

A SAE is defined as an AE meeting one of the following outcomes:

- Death
- Life-threatening event
- Inpatient hospitalization or prolongation of existing hospitalization
- Persistent or significant disability/incapacity or substantial disruption of the ability to conduct normal life functions
- Congenital anomaly or birth defect

Any other important medical event that may not result in one of the above outcomes may be considered a SAE when, based upon appropriate medical judgment, the event may jeopardize the participant and may require medical or surgical intervention to prevent one of the outcomes listed above.

A life-threatening AE is any AE that places the subject, in the view of the Investigator, at immediate risk of death from the AE as it occurred. It does not include an AE that, had it occurred in a more severe form, might have caused death.

16.3 Events of Clinical Interest

The following are considered events of clinical interest (ECIs) if they occur after dosing, and must be reported by the site when it becomes aware of the ECI:

- ALT or AST $>8 \times$ ULN, if new compared to Baseline, confirmed by repeat testing
- ALT or AST $>5 \times$ ULN for more than 2 weeks and if new compared to Baseline, confirmed by repeat testing

- ALT or AST >3 x ULN and total bilirubin >2 x ULN and if new compared to Baseline, confirmed by repeat testing
- ALT or AST >3 x ULN, confirmed by repeat testing, with the appearance of fatigue, nausea, vomiting, right upper quadrant pain or tenderness, fever, rash, and/or eosinophilia (>5%)]

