1. Subject has an invasive fungal disease with central nervous system involvement unless the subject is planned to receive combination therapy with ibrexafungerp and other antifungal.
2. Subject has an inappropriately controlled fungal disease source (e.g., persistent catheters, devices, identified undrained abscess) that is likely to be the source of the fungal disease.
3. Subject is hemodynamically unstable and/or requiring vasopressor medication for blood pressure support.
4. Subject has abnormal liver test parameters: AST or ALT >10 x ULN and/or total bilirubin >5 x ULN.
Note: Subjects with unconjugated hyperbilirubinemia with a diagnosis of Gilbert's disease **are not excluded.**
5. Subject is unlikely to survive 30 days.

Study Drugs:

Ibrexafungerp citrate drug product for oral administration will be supplied as compressed oral tablets containing 250 mg of ibrexafungerp active ingredient on a free base basis. In addition to the active ingredient, the oral tablet formulation also contains silicified microcrystalline cellulose, crospovidone, mannitol, colloidal silicon dioxide, magnesium stearate (non-bovine), and butylated hydroxyanisole. Ibrexafungerp is packaged in bottles containing 30 tablets.

Ibrexafungerp tablets are to be stored at room temperature: between 15°C and 25°C with allowable limited excursions of up to 30°C.

Randomized Treatment Groups: This is an open-label, non-comparator, single-arm study. All subjects will receive ibrexafungerp monotherapy except subjects with refractory or relapsing invasive pulmonary aspergillosis (IPA), mucormycosis or other molds with unpredictable ibrexafungerp activity, who will receive combination therapy. Combination therapy may also be administered to other subjects based on Investigator's judgement and contingent on Sponsor approval. Subjects will receive ibrexafungerp on an inpatient or outpatient basis, as needed for each fungal disease.

Ibrexafungerp Monotherapy for All fungal Diseases, Excluding VVC

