11.1 Inclusion Criteria

Subjects must fulfill all of the following criteria at Screening and/or Baseline to be eligible for study admission:

1. Subject is a male or female adult ≥ 18 years of age on the day the study informed consent form (ICF) is signed.
2. Subject has a documented eligible fungal disease that has been refractory or resistant to SOC, has relapsed after, or the subject has intolerance to or demonstrated toxicities resulting from an approved SOC antifungal treatment (as defined in [Table 5](#)). The subject is also eligible if, in the judgement of the Investigator, long-term IV antifungal therapy is not feasible or desirable due to clinical (isolate is resistant to or has a high MIC and is unlikely to respond to antifungal SOC) or logistical circumstances or if other antifungal alternatives are not appropriate.

Table 5 Eligible Fungal Diseases

Fungal Disease	Diagnostic Criteria	Eligibility Criteria

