- b: **Toxicity** for any of the eligible diseases above is defined as the degree to which a substance (antifungals) can damage an individual as well as cause a negative effect on a substructure of an individual such as a system or organ. The toxicity should be of a severity or prognosis such that, as per the Investigator's judgement, it is in the best interest of the subject to modify his/her antifungal therapy. Example of toxicities include:
 - Nephrotoxicity defined as elevation of serum creatinine level by 2 times the baseline value or any value above the upper limit of normal (ULN), in a repeat test at least 24 hours apart.
 - Hepatotoxicity defined as elevation of aspartate aminotransferase (AST) and alanine aminotransferase (ALT) >5 times ULN.
 - Other events not related to the subject's condition and that started after initiation of the standard antifungal agent, such as visual disturbances, cutaneous reactions, neurological reactions, histamine reactions, etc.
 - Drug-drug interactions of the standard antifungal agent with other therapies being received by the subject, which are either associated with a documented toxicity or are likely to result in toxicity.
- c: **Relapse** is defined as deterioration or worsening of a fungal disease after an initial improvement to therapy.

3. Subject is able to tolerate medication orally or through a nasogastric (NG) tube or percutaneous endoscopic gastrostomy (PEG) tube.
4. Subject and/or legal guardian is/are able to understand and sign a written ICF, which must be obtained prior to treatment and any study-related procedures.
5. Subject and/or legal guardian is able to understand and sign a consent or authorization form, which shall permit the use, disclosure and transfer of the subject's personal health information. (e.g., in the US, a Health Insurance Portability and Accountability Act [HIPAA] authorization form).
6. Subject and/or legal guardian is able to understand and follow all study-related procedures including study drug administration.
7. Subject is not pregnant and is highly unlikely to become pregnant or to impregnate a partner since he/she meets at least one of the following criteria:

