11.2 Exclusion Criteria

A subject will be excluded from participation in the study if he or she meets any of the following exclusion criteria at Screening and/or Baseline:

1. Subject has an invasive fungal disease with central nervous system involvement unless the subject is planned to receive combination therapy with ibrexafungerp and other antifungal.
2. Subject has an inappropriately controlled fungal disease source (e.g., persistent catheters, devices, identified undrained abscess) that is likely to be the source of the fungal disease.
3. Subject is hemodynamically unstable and/or requiring vasopressor medication for blood pressure support.
4. Subject has abnormal liver test parameters: AST or ALT $>10 \times$ ULN and/or total bilirubin $>5 \times$ ULN.

Note: Subjects with unconjugated hyperbilirubinemia with a diagnosis of Gilbert's disease **are not excluded.**

5. Subject is unlikely to survive 30 days.
6. Subject has any other condition or laboratory abnormality that, in the judgment of the Investigator, would put the subject at unacceptable risk for participation in the study or may interfere with the assessments included in the study.
7. Subject requires treatment with the prohibited medications.
8. Subject has known hypersensitivity to ibrexafungerp.
9. Subject is pregnant or lactating.
10. Subject has received any other investigational drug (i.e., new chemical entity) within at least 30 days (or 5 and a half half-lives of the investigational product) before signing the ICF.
11. Subject is an employee of SCYNEXIS, Inc., the Investigator, or contract research organization involved in the study, or an immediate family member (partner, offspring, parents, siblings, or sibling's offspring) of an employee involved in the study.

12. Subject or legal representative is/are unable to provide written informed consent for any reason.
13. Subject is unlikely to comply with protocol requirements.

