### **8.2.2 Events of Clinical Interest**

The frequency and percentage of subjects with the following elevations will be summarized at any post-baseline visit:

- ALT or AST  $> 8 \times$  the upper limit of normal (ULN);
- ALT or AST  $> 5 \times$  ULN if new compared to Baseline;
- ALT or AST  $> 3 \times$  ULN and total bilirubin  $> 2 \times$  ULN if new compared to Baseline;
- ALT or AST  $> 3 \times$  ULN.

If subjects meet the criterion ALT or AST  $> 3 \times$  ULN, the additional summary of the frequency and percentage of subjects with ALT or AST  $> 3 \times$  ULN, confirmed by repeat test, and with the appearance of fatigue, nausea, vomiting, right upper quadrant pain or tenderness, fever, rash, and/or eosinophilia ( $> 5\%$ ) will be provided.

A listing will be provided for the above elevations, including the actual measurement of ALT, AST, and total bilirubin, and their reference high limits.

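### For subjects already above a liver limit at baseline, the 'new' condition in the liver ECIs and the rows of the SAP table cannot tell worsening from stable elevation

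*Protocol*

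**What the plan says.** **Entry.** Exclusion criterion 4 (Protocol 11.2, repeated in the Synopsis) reads "Subject has abnormal liver test parameters: AST or ALT >10 x ULN and/or total bilirubin >5 x ULN", so values up to and including those limits are admitted. Subjects with unconjugated hyperbilirubinemia due to Gilbert's disease are exempt. A subject may also qualify because "the subject has intolerance to or demonstrated toxicities resulting from an approved SOC antifungal treatment". Table 5, footnote b, gives this example: "Hepatotoxicity defined as elevation of aspartate aminotransferase (AST) and alanine aminotransferase (ALT) >5 times ULN".

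**Protocol 16.3** lists four liver ECIs that sites must report:
- ECI 1: ALT or AST >8x ULN, "if new compared to Baseline, confirmed by repeat testing".
- ECI 2: ALT or AST >5x ULN "for more than 2 weeks and if new compared to Baseline, confirmed by repeat testing".
- ECI 3: "ALT or AST >3 x ULN and total bilirubin >2 x ULN and if new compared to Baseline, confirmed by repeat testing".
- ECI 4: ALT or AST >3x ULN, confirmed, with the appearance of listed symptoms, rash or eosinophilia. It carries no 'new' condition.

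The protocol does not define 'new'.

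**SAP 8.2.2** states: "The frequency and percentage of subjects with the following elevations will be summarized at any post-baseline visit". Its four rows differ from the ECIs:
- Row A: >8x, without 'new'.
- Row B: >5x, with 'new' but without the two-week duration.
- Row C: >3x with bilirubin >2x, with 'new'.
- Row D: >3x alone, without 'new'.

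A further summary covers >3x with symptoms, and a listing gives the actual ALT, AST and bilirubin values. SAP 8.2 classifies laboratory results as Low, Normal or High for the shift tables.

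**The concern.** The limits in ECIs 1 to 3 all lie below the entry ceilings, so subjects can be enrolled who already exceed them. For those subjects the only link to baseline is the word 'new', which asks whether a limit was crossed and not how far the value moved. Safety is a primary objective. Subjects with raised liver tests at entry are those in whom a reader most needs to tell drug-related worsening from the condition they came in with. A criterion already met at entry cannot make that distinction.

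**Working it through.** The plan gives no figure to reproduce; the check is one of logic.

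**Rule applied.** A criterion counts as an event if it is met on treatment and either it has no 'new' condition or it was not already met at baseline. SAP section 3 defines baseline as the last non-missing value up to the first dose. For ECI 2, a baseline value >5x is taken as already meeting the criterion, whatever its prior duration. The >2-week requirement is assumed satisfied on treatment, and results are assumed confirmed. The subject has no symptoms, so ECI 4 is not met. The on-treatment values are illustrative assumptions.

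Values are multiples of ULN, shown as ALT / bilirubin:

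| Baseline | On treatment | Protocol ECIs 1–3 met | SAP rows counted |
|---|---|---|---|
| 1 / 1 | 20 / 8 | 1, 2, 3 | A, B, C, D |
| 4 / 3 | 20 / 8 | 1, 2 | A, B, D |
| 6 / 1 | 20 / 8 | 1, 3 | A, C, D |
| 6 / 3 | 20 / 8 | 1 | A, D |
| 9 / 1 | 20 / 8 | 3 | A, C, D |
| 9 / 1 | 20 / 1 | none | A, D |
| 9 / 3 | 20 / 8 | none | A, D |
| 10 / 5 | 20 / 8 | none | A, D |
| 9 / 3 | 9 / 3 (stable) | none | A, D |

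**When all three are closed.** ECI 1 is closed if baseline ALT/AST >8x, ECI 2 if >5x, and ECI 3 if >3x with bilirubin >2x. The three hold together exactly when ALT/AST >8x and bilirubin >2x. Within the entry limits that means ALT/AST above 8x up to 10x with bilirubin above 2x up to 5x (higher under the Gilbert's exemption). A 9x subject with normal bilirubin can still reach ECI 3, but only if bilirubin also rises; the 9 / 1 to 20 / 1 line meets none of the three.

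**SAP rows.** Compare 9 / 3 rising to 20 / 8 with 9 / 3 staying at 9 / 3: the rows counted are identical. For a subject above a row's limit at baseline, rows B and C return a non-event whether or not the values worsen. Rows A and D return an event for as long as any post-baseline value stays above the limit, again whether or not the values worsen.

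**Shift tables.** ALT of 9x and of 20x are both above the normal range, so the cell is High to High.

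**Size.** The documents do not give the number entering above any limit. Purely as an assumption, if 2% to 10% of 220 subjects entered above 5x ULN, that is 0.02 × 220 = 4.4 to 0.10 × 220 = 22, or about 4 to 22. These are subjects who could not count in row B; how many of them would worsen is unknown.

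**The case against.** The strongest reply is that this is a gap in a label, not in hepatic safety capture. Protocol 16.1 makes any laboratory abnormality the investigator judges clinically significant an AE and allows worsening of a condition present at baseline to be one. Protocol 16.10 requires SAEs within 24 hours. Changes from baseline in laboratory values are summarized, and the SAP 8.2.2 listing would show a large rise. All of this stands. But AE reporting of a laboratory value rests on judgement, change summaries are not split by baseline status, and a listing is not a summary.

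Four stronger inferences are tempting, and the documents do not support them.

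- *The liver ECIs are switched off for subjects enrolled for hepatotoxicity.* Footnote b describes toxicity from the prior antifungal. Protocol 7.2 includes history and anticipation of toxicity, and Table 5 speaks of current or past toxicity for dimorphic fungi. The elevation need not persist at baseline.
- *Subjects with raised baselines are lost from all three ECIs.* The block works criterion by criterion, as the table shows, and ECI 4 stays open.
- *The SAP table understates hepatic events overall.* Rows B and C can under-count worsening in these subjects, but rows A and D count stable elevations. The errors run in both directions.
- *ECI 4 is faulty because it lacks a 'new' condition.* It requires symptoms, rash or eosinophilia to appear, and ECIs must occur after dosing. Leaving the enzyme part unrestricted is a choice in favour of sensitivity, not an error.

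One could also read 'new' loosely, as any new rise. The text gives no size for such a rise, so sites could not apply that reading uniformly.

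**Conclusion.** The point holds for subjects who already meet a given criterion at baseline. On the literal reading of 'new', that same protocol ECI is unavailable to them, and each SAP 8.2.2 row classifies them by where they started and not by whether they worsened. The shift tables do not fill the gap. The protocol and SAP also disagree on which criteria carry the condition: three in 16.3, two in 8.2.2.

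The conclusion rests on 'new' meaning that the same criterion was not met at baseline. For ECI 2 it also rests on a baseline value >5x counting as already present without proof of two weeks' duration. If each component of ECI 3 had to be new, the block would be wider, reaching anyone entering with ALT/AST >3x or bilirubin >2x alone. The size is unknown, and the range of 4 to 22 is an assumption. The defect lies in flagging and tabulation; other routes for reporting a worsening liver test remain.

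**What to change.** **SAP 8.2.2.** For each limit, report the number of subjects already above it at baseline and present them separately from those at or below it. For those above, tabulate the ratio of the post-baseline peak to the baseline value for ALT, AST and total bilirubin, each separately. This uses data already collected and works even if 16.3 can no longer be amended.

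**Protocol 16.3 and SAP 8.2.2.** Reconcile which criteria carry the 'new' condition and define the word. State in 16.3 how worsening is reported for a subject already above a limit at baseline, leaving any multiple of baseline to the sponsor. This concerns reporting and analysis only.

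**Cost.** One extra table, a short clarification in 16.3, and possibly a few more reportable ECIs.
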